10.6.2.2 Additional Secondary Efficacy Analyses

For secondary efficacy analyses, KM methods will be used to estimate curves for time to event secondary variables. Counts and percentages will be used to describe categorical secondary variables. Secondary efficacy analyses will be performed on the ITT population unless otherwise specified.

Platelet response (HI-P) is defined according to IWG 2006 criteria (Cheson, 2006; Appendix D). HI-P rates will be summarized and compared between the two treatment groups using the same methods as the primary endpoint (see Section 10.6.1).

RBC transfusion independence for 84 days is defined as the absence of any RBC transfusion during any consecutive “rolling” 84 days during the treatment period, ie, Day 1 to 84, Day 2 to 85, Days 3 to 86, etc. Frequency cross-tabulations of RBC transfusion dependency status for 84 days at baseline versus on-treatment will be presented by treatment group.

Duration of RBC transfusion independence for 56 days will be determined only for subjects who achieve RBC transfusion independence on treatment. Duration of RBC transfusion independence is defined as the time from the date transfusion independence is first observed (day 1 of 56 or more days without a transfusion) until the date the subject has a subsequently documented transfusion of RBC. Subjects who maintain RBC transfusion independence through the end of the treatment period will be censored at the date of treatment discontinuation or death, whichever occurs first. Duration of RBC transfusion independence curves will be estimated using KM methods and treatment groups will be compared using a log-rank test.

Time to RBC transfusion independence for 56 days is defined as the time between randomization and the date onset of transfusion independence is first observed (ie, Day 1 of 56 without any RBC transfusions). Subjects who do not achieve RBC transfusion independence during the treatment period will be censored at the date of treatment discontinuation or death, whichever occurs first. Time to RBC transfusion independence curves will be estimated using KM methods and treatment groups will be compared using a log-rank test. A Cox proportional hazards model will be used to estimate the corresponding hazard ratio and 95% CI.

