10.1. Analysis of Primary Efficacy Endpoint

The primary efficacy endpoint of RBC transfusion independence is defined as the absence of any RBC transfusion during any consecutive "rolling" 56 days within the treatment period. A subject who did not receive any RBC transfusion during a consecutive rolling 56 days (i.e., day 1 to day 56, day 2 to day 57) will be considered as a 56-day RBC transfusion independent responder. Subjects without achieving the response as defined above, subjects with less than 56 days of assessment during the double-blind treatment period, and subjects who had average baseline RBC transfusion units less than 2 units per 28 days (as defined in Section 8.2) will be counted as non-responders.

All RBC transfusion records on or after randomization within the evaluation period will be used to assess the response for each subject. In other words, the days after the end of the evaluation period will not contribute to a rolling period. The end date of the evaluation period is defined as:

- For a subject who discontinues the treatment,

- If the subject doesn't receive a subsequent MDS treatment, use the date of end of treatment visit;
- If the subject receives a subsequent MDS treatment, use the start date of the subsequent MDS treatment – 1 day, or the date of end of treatment visit, whichever is earlier;
- For a subject who is still on-treatment at the time of the database lock for the primary analysis, the subject's latest available assessment date in the database (from AE, vital sign, local and central lab, study drug records, efficacy assessments) will be used.

The 56-day rolling period for the RBS transfusion independent assessment starts on the date of randomization.

Note if the interval between the last RBC transfusion in the evaluation period (if there is at least one RBC transfusion during the evaluation period) and the end date of the evaluation period is less than 56 days, this rolling period, which is less than 56 days, won't be considered as meeting the transfusion independence criteria even though there is no RBC transfusion in it. The day on which the transfusion is received will not contribute to the 56-day without receiving RBC transfusion rolling period.

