10.2.5. Time to RBC transfusion independence of ≥ 56 days (8 weeks)

Time to RBC transfusion independence of ≥ 56 days is defined as the time between randomization and the date onset of transfusion independence is first observed (ie, Day 1 of 56 without any RBC transfusions). Subjects who do not achieve RBC transfusion independence

during the treatment period will be censored at the end date of evaluation period which is defined in Section 10.1. In case a subject has more than one rolling periods which meet the independence criteria, the time to the first rolling period will be used in the analysis. Time to RBC transfusion independence curves will be estimated using KM methods and treatment groups will be compared using a stratified log-rank test. A stratified Cox proportional hazards model will be used to estimate the corresponding hazard ratio and 95% CI. Time to RBC transfusion independence (in month) for at least 56 days will also be summarized using descriptive statistics based on subjects who achieve the response.

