10.2.9. Time to AML Progression

Time to AML Progression is defined as the time from the date of randomization until the date the subject has documented progression to AML. For subjects who have progression to AML documented in central lab report, the earliest sample collection date with the diagnosis of “s-AML arising from previous MDS” will be used as the date to AML progression (in case multiple records are available for the samples collected on the same day, the records with the latest report date will be used). For subjects who only have progression to AML documented in the Follow-up Status CRF, the date of progression from the CRF page will be used. Subjects who do not progress to AML will be censored at the date of last follow-up or at date of death. Time to AML progression curves will be estimated using KM methods and treatment groups will be compared using a log-rank test. KM estimates for median time to AML progression and the 1-year and 2-year AML progression rate will be summarized for each treatment group. A Cox proportional hazards model will be used to estimate the corresponding hazard ratio and 95% CI. A competing risk analysis, treating death as a competing risk for AML progression, will be conducted for exploratory purposes.

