10.2.14. Time to platelet transfusion independence

Time to platelet transfusion independence is defined as the time between randomization and the first documented date of onset of transfusion independence (ie, Day 1 of 56 without any platelet transfusions). The derivation is similar as for the time to RBC transfusion independence of ≥ 56 days (Section [10.2.5](#)), except using platelet transfusion. Subjects who are platelet transfusion independent at baseline will be excluded from the analysis. Time to platelet transfusion independence will be analyzed descriptively using KM methods. Time to platelet transfusion

independence (in month) for at least 56 days will also be summarized using descriptive statistics based on subjects who achieve the response.

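### Kaplan-Meier with death censored overstates the 1- and 2-year AML rates, and the time-to-transfusion-independence curves overstate response because subjects who stop or die are censored

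*SAP*

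**What the plan says.** **AML.** SAP 10.2.9 states: "KM estimates for median time to AML progression and the 1-year and 2-year AML progression rate will be summarized for each treatment group". Subjects without AML are censored at last follow-up or at death. The same section adds a competing-risk analysis with death as the competing event, for exploratory purposes, and does not name its estimator. SAP 10.2.8 also reports a crude number and percentage progressing.

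**Time to RBC transfusion independence.** SAP 10.2.5 (56 days) specifies: "Time to RBC transfusion independence curves will be estimated using KM methods", with a stratified log-rank test, a stratified Cox model and a descriptive summary of time among responders. Subjects without a response "during the treatment period will be censored at the end date of evaluation period which is defined in Section 10.1". For a subject who discontinues without later MDS therapy, SAP 10.1 says to "use the date of end of treatment visit"; with later MDS therapy, the period ends the day before that therapy starts, if this is earlier. SAP 10.1 also says that days beyond this point cannot count toward a response window. Protocol 10.6.2.2 names the censoring events outright: non-achievers "will be censored at the date of treatment discontinuation or death, whichever occurs first". SAP 10.2.7 (84 days) follows 10.2.5.

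**Platelets.** SAP 10.2.14 carries the derivation over: "Time to platelet transfusion independence will be analyzed descriptively using KM methods".

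**Responder proportion.** In the primary analysis (SAP 10.1), non-achievers and "subjects with less than 56 days of assessment during the double-blind treatment period" count as non-responders.

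**The concern.** Censoring treats a subject as still able to have the event later. A subject who has died cannot progress to AML. A subject whose evaluation period has closed cannot, by the SAP's own definition, reach on-treatment transfusion independence. These are competing events, and one minus Kaplan-Meier then describes a hypothetical population in which nobody dies or stops.

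Two uses are affected.

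- **AML.** Protocol 4.2 justifies the placebo arm partly by the need to show that AML does not occur more often or earlier on treatment. The 1- and 2-year rates will be read as the share of patients who develop AML. Mortality is heavy: the plan expects 205 deaths among 216 subjects.
- **Transfusion independence.** The same subject is a non-responder in the primary proportion and censored in the curve, so a plotted curve will sit above the reported rate. Stopping is also tied to lack of benefit: the Cycle 6 disease status assessment discontinues subjects who meet none of the continuation criteria.

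The overstatement can differ by arm. Protocol 1.4.1 reports an imbalance in deaths between the groups, with most deaths on azacitidine in the first 56 days of treatment.

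**Working it through.** **1. Check of the death hazards.** The documents give no figure for the bias itself, so the survival assumptions that feed the calculation are checked first. SAP 4.4 gives median OS of 18 and 25.7 months, hazard ratio 0.70, 205 deaths, two-sided alpha 0.05 and about 72% power.

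- 18/25.7 = 0.700.
- Power = Φ(√205/2 × |ln 0.70| − 1.96) = Φ(2.553 − 1.960) = Φ(0.593) = 72.4%. The stated figure is reproduced.

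**2. Direction, without any model.** At each event time both estimators add (probability of being event-free just before) × (events / number at risk). Kaplan-Meier uses freedom from the event of interest alone. Aalen-Johansen uses freedom from the event and from the competing event. The second is never larger, so one minus Kaplan-Meier is never below the cumulative incidence, and it is above it once an event of interest follows a competing one.

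**3. Formulas for size.** With constant hazards a (event) and m (competing event):

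- 1 − KM(t) = 1 − exp(−a t)
- CIF(t) = a/(a+m) × [1 − exp(−(a+m) t)]

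**4. AML.** Assumed a = −ln(0.75)/3.3 = 0.0872 per year, from the INT-1 figure in Protocol 1.1 (25% at 3.3 years). From the OS medians, m = ln 2/1.5 = 0.462 per year on placebo and ln 2/(25.7/12) = 0.324 on azacitidine.

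| Arm | Year | 1 − KM | Cumulative incidence |
|---|---|---|---|
| Placebo | 1 | 8.3% | 6.7% |
| Placebo | 2 | 16.0% | 10.6% |
| Azacitidine | 1 | 8.3% | 7.1% |
| Azacitidine | 2 | 16.0% | 11.9% |

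Placebo at 2 years, written out: 1 − exp(−0.174) = 0.160, against (0.0872/0.549) × [1 − exp(−1.099)] = 0.159 × 0.667 = 0.106.

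OS deaths include deaths after AML, so m is somewhat too high as a hazard of death before AML. At the opposite extreme, with death immediate on AML, m = 0.462 − 0.087 = 0.375. Placebo at 2 years then becomes (0.0872/0.462) × [1 − exp(−0.924)] = 0.189 × 0.603 = 11.4%. The placebo range is therefore 10.6 to 11.4%.

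The AML hazard in this population is not known. Varying a from the Low-risk value (25% at 9.4 years) to three times the INT-1 value, with m from the OS medians, gives an excess of 0.4 to 4.4 points at 1 year and 1.6 to 13.1 points at 2 years. The ratio is about 1.2 at 1 year and 1.3 to 1.5 at 2 years.

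**5. Transfusion independence.** The response rates 0.30, 0.15 and 0.05 come from SAP 4.4. The median time to discontinuation or death is in neither document, so 4, 6 and 12 months are assumed. For each, a is solved so that CIF(12 months) equals the true rate, and 1 − KM(12 months) is then read off.

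| True 12-month probability | Median 4 months | 6 months | 12 months |
|---|---|---|---|
| 30% | 62% | 51% | 40% |
| 15% | 33% | 27% | 20% |
| 5% | 12% | 9% | 7% |

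First cell: m = ln 2/4 = 0.173 and a = 0.0797 per month give CIF = (0.0797/0.253) × [1 − exp(−3.04)] = 0.30, and 1 − exp(−0.956) = 0.62.

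**The case against.** The strongest reply is that little rests on these outputs. Four parts of it stand, and each limits what a reader might otherwise infer.

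- **A reader might infer that AML is also censored at treatment discontinuation.** It is not. SAP 10.2.9 lists only last follow-up and death, and Protocol 4.1.3 continues AML follow-up after discontinuation. Appendix J shortens follow-up for Extension Phase participants, but that does not turn discontinuation into a censoring rule.
- **A reader might infer that competing risks are ignored for AML.** They are not, since an analysis is planned. What remains is that the listed 1- and 2-year rates are Kaplan-Meier and the appropriate estimate is relegated to exploratory status. The crude percentage in SAP 10.2.8 does not fill the gap, because it ignores unequal follow-up and is not a rate at 1 or 2 years.
- **A reader might infer that the estimated probability of transfusion independence is biased.** The plan takes that probability from the ITT proportion, and asks for no landmark rate and no median from the time-to-response curve. The overstatement lies in how the plotted curve reads.
- **A reader might infer that the between-arm tests are invalid.** Log-rank and Cox remain valid as comparisons of cause-specific hazards. SAP 10.2 controls alpha only for the primary endpoint and OS, and time to platelet independence is descriptive.

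The sizes also rest on assumptions. INT-1 in general is not this population; Protocol 1.1 links more severe thrombocytopenia with shorter time to AML. Response onset is back-dated to the first day of the window, so a constant hazard is rough for transfusion independence. The direction depends on none of these assumptions.

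**Conclusion.** The point holds for description, not for inference. The 1- and 2-year AML rates in SAP 10.2.9 will overstate the share of patients who progress: at 2 years by about 5 points on placebo (16.0% against 10.6 to 11.4%) and about 4 on azacitidine (16.0% against about 11.9%), under constant hazards, an INT-1 AML hazard and the SAP's OS medians. In that example the AML hazards are equal, so Kaplan-Meier shows identical arms although the proportions who develop AML differ.

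The curves in SAP 10.2.5, 10.2.7 and 10.2.14 will overstate the probability of response. The RBC curves will not match the ITT responder proportions. At a true 30% the excess is roughly 10 to 32 points, depending wholly on a discontinuation rate that the documents do not supply.

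No confirmatory test and no primary-endpoint estimate changes.

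**What to change.** - **SAP 10.2.9:** report the AML curves and the 1- and 2-year rates as Aalen-Johansen cumulative incidence with death as the competing event, moving the analysis already planned out of exploratory status and naming its estimator.
- **SAP 10.2.5, 10.2.7 and 10.2.14:** show cumulative-incidence curves. The competing event is death, or the end of the evaluation period through treatment discontinuation or subsequent MDS therapy. Censor only subjects still on treatment at data cut-off.
- **Keep** the planned log-rank and Cox analyses where they are specified, labelled as cause-specific.

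The cost is a few lines of SAP text and a standard procedure call. It needs no new data and no change to alpha. The rationale for Protocol Amendment 6.0 says that the primary analysis report is already final, so the transfusion-independence curves would be supplementary outputs. The AML change can still be written into the plan for the final AML analysis, which SAP section 2 defers to a later date.

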10.2.6. Duration of RBC transfusion independence of ≥ 84 days (12 weeks)

Duration of RBC transfusion independence will be analyzed only for subjects who achieve RBC transfusion independence of ≥ 84 days on treatment. The calculation and analysis are similar as for the duration of RBC transfusion independence of ≥ 56 days (Section 10.2.4).

10.2.7. Time to RBC transfusion independence of ≥ 84 days (12 weeks)

Time to RBC transfusion independence of ≥ 84 days is defined as the time between randomization and the date onset of transfusion independence is first observed (ie, Day 1 of 84 without any RBC transfusions). The derivation and analysis are similar as for the time to RBC transfusion independence of ≥ 56 days (Section 10.2.5). Time to RBC transfusion independence (in month) for at least 84 days will also be summarized using descriptive statistics based on subjects who achieve the response.

10.2.8. Progression to AML

Progression to AML will be documented in central lab report or Follow-up Status CRF. Subjects who have a diagnosis of “s-AML arising from previous MDS” documented in central lab report (in case multiple records are available for the bone marrow and/or peripheral blood samples collected on the same day, the records with the latest report date will be used), or subjects with progression to AML documented in the Follow-up Status CRF will be identified. Number and percentage of subjects progressing to AML will be presented by treatment group.

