6.6.2 Progression to AML and Second Primary Malignancies

Progression to AML and second primary malignancies will be monitored as events of interest and should be included as part of the assessment of AEs throughout the course of the study. Investigators are to report progression to AML and any second primary malignancy, regardless of causal relationship to IP (oral azacitidine or placebo), occurring at any time from signing of informed consent until death, lost to follow-up, or withdrawal of consent for further data collection. Events of progression to AML and second primary malignancy are to be reported as a serious adverse event (SAEs; considered to be an adverse event of special interest (AESI) even if no other seriousness criteria apply). This information must also be documented on the appropriate pages of the CRF and in the subject's source documents. Documentation on the diagnosis of progression to AML and/or the second primary malignancy (eg, any confirmatory histology or cytology results, X-rays, CT scans, etc.) must be provided at the time of reporting as an SAE. Refer to [Section 11.2](#) for evaluation of AEs.

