Duration of RBC transfusion independence for 84 days will be determined only for subjects who achieve RBC transfusion independence on treatment. Duration of RBC transfusion independence is defined as the time from the date transfusion independence is first observed (day 1 of 84 or more days without a transfusion) until the date the subject has a subsequently documented transfusion of RBC. Subjects who maintain RBC transfusion independence through the end of the treatment period will be censored at the date of treatment discontinuation or death, whichever occurs first. Duration of RBC transfusion independence curves will be estimated using KM methods and treatment groups will be compared using a log-rank test.

Time to RBC transfusion independence for 84 days is defined as the time between randomization and the date onset of transfusion independence is first observed (ie, Day 1 of 84 without any RBC transfusions). Subjects who do not achieve RBC transfusion independence during the treatment period will be censored at the date of treatment discontinuation or death, whichever occurs first. Time to RBC transfusion independence curves will be estimated using KM methods and treatment groups will be compared using a log-rank test. A Cox proportional hazards model will be used to estimate the corresponding hazard ratio and 95% CI.

Progression to AML is defined as bone marrow blast count $\geq 20\%$. Number and percentage of subjects progressing to AML will be presented by treatment group.

Time to AML Progression is defined as the time from the date of randomization until the date the subject has documented progression to AML. Subjects who do not progress to AML will be censored at the date of last follow-up or at date of death. Time to AML progression curves will be estimated using KM methods and treatment groups will be compared using a log-rank test. KM estimates for median time to AML progression and the 1-year and 2-year AML progression rate will be summarized for each treatment group. A Cox proportional hazards model will be used to estimate the corresponding hazard ratio and 95% CI. [REDACTED]

Erythroid response (HI-E) is defined according to IWG 2006 criteria ([Cheson, 2006](#); [Appendix D](#)). HI-E response will be presented descriptively, by treatment group, using counts and percents.

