11.1.2.2. Progression to AML

Progression to AML will be identified as treatment-emergent AESI and will be summarized by treatment group.

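### The AML endpoint in SAP 10.2.8 and 10.2.9 leaves out SAE-reported AML and the protocol's 20% blast threshold, and lets a later central date displace an earlier CRF date

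*SAP*

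**What the plan says.** **Event.** SAP 10.2.8: "Progression to AML will be documented in central lab report or Follow-up Status CRF". The section then gives two routes. One is a central report with a specific diagnosis of secondary AML arising from prior MDS (below, the s-AML diagnosis). The other is the CRF: "or subjects with progression to AML documented in the Follow-up Status CRF will be identified".

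**Date.** SAP 10.2.9: "For subjects who have progression to AML documented in central lab report, the earliest sample collection date with the diagnosis of" s-AML gives the event date. The CRF date is the fallback: "For subjects who only have progression to AML documented in the Follow-up Status CRF, the date of progression from the CRF page will be used". Everyone else is censored at last follow-up or death.

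**Protocol definition.** Protocol 10.6.2.2: "Progression to AML is defined as bone marrow blast count" of at least 20%.

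**Protocol reporting.** Protocol 6.6.2: "Events of progression to AML and second primary malignancy are to be reported as a serious adverse event". Sections 6.6.2 and 11.5 apply this from consent until death, loss to follow-up or withdrawal of consent. They ask for diagnostic documentation and for entry on the relevant CRF pages, which they do not name.

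**Safety summary.** SAP 11.1.2.2: "Progression to AML will be identified as treatment-emergent AESI and will be summarized by treatment group".

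**Declared change.** SAP Section 16 lists the new AML sources among its changes to the protocol's statistical section. It gives no reason. It does not address a blast count over the threshold without the diagnosis, or an SAE without a Follow-up Status entry.

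**The concern.** The SAP endpoint uses neither the protocol's definition of AML progression nor the protocol's mandatory reporting route. A case that satisfies the protocol can therefore fail to be an event in the SAP, and it then contributes AML-free time up to last follow-up or death.

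The proportion progressing to AML and the time to AML are both secondary endpoints. Protocol 4.2 also gives AML as a reason for having a placebo arm: the trial should show that AML is not induced more often or earlier than the underlying disease would produce. An endpoint that can drop or post-date cases is less able to answer that question.

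**Working it through.** The documents give no AML event rate, event count or power, so there is no stated figure to reproduce. The check is to apply the SAP rule to possible patterns of records and compare it with the earliest qualifying source.

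**Rules compared**

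- SAP rule: the date of the earliest central sample with the s-AML diagnosis, if there is one; otherwise the Follow-up Status CRF date; otherwise no event.
- Comparison rule: the earliest of central s-AML diagnosis, central marrow blasts of at least 20%, Follow-up Status CRF, and SAE.

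**Marrow schedule.** Protocol Table 1 places marrows on Day 1 of Cycles 3, 6 and 12 and then every 6 months (for example Cycles 18 and 24), with a 28-day cycle. With no delays, Day 1 of Cycle k is study day (k − 1) × 28 + 1:

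- Cycles 3, 6, 12, 18, 24: days 57, 141, 309, 477, 645.
- Gap from Cycle 3 to 6: (6 − 3) × 28 = 84 days.
- Gap from Cycle 6 to 12, and each later gap: 6 × 28 = 168 days.

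Table 1 schedules no marrow at Treatment Discontinuation or in Follow-up.

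**Hypothetical subjects (study days)**

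| Records | SAP rule | Earliest source | Difference |
|---|---|---|---|
| CRF day 200, central s-AML day 309 | 309 | 200 | 309 − 200 = 109 days late |
| SAE only, day 200 | no event | 200 | missed |
| Central blasts ≥20% day 141 without the diagnosis, s-AML day 309 | 309 | 141 | 309 − 141 = 168 days late |
| Central blasts ≥20% day 141 only | no event | 141 | missed |
| Central s-AML day 141, CRF day 200 | 141 | 141 | none |

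The first row follows from the word only in the CRF date rule together with the absence of any earliest-of-sources rule; the SAP does not say outright that a later central date wins. If the next central sample is the scheduled one, the delay can reach about 168 days. Cycle delays would lengthen it and unscheduled central marrows would shorten it.

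**Are the missing data available?** SAE reports are mandatory. Central marrow blast percentages are already read numerically in SAP Appendix F to derive remission and disease progression. Both inputs exist and are simply not used in 10.2.8.

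**The case against.** The strongest reply is that the rule is a disclosed choice and that the affected cases may hardly exist.

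- **Disclosure.** A reader might infer an undeclared departure from the protocol. The documents do not support that, because SAP Section 16 lists the change. What is missing is a reason and a rule for discordant records.
- **Blasts of 20% or more without the diagnosis.** Protocol Appendix A ends the highest MDS blast category at 19%, and Appendix D notes that 20–30% is AML under WHO. A central reviewer would ordinarily give the AML diagnosis, so this case should be uncommon.
- **Unscheduled marrows.** Protocol 6.7.3 provides for clinically indicated marrows and refers sample submission to the Central Laboratory Manual. The protocol summary has the central reviewer assessing marrows during the study. The 84- and 168-day gaps are therefore not typical delays.
- **SAE-only cases.** The protocol also requires CRF entry, and Section 6.14 follows discontinued subjects for AML monthly for a year and then every three months. The CRF itself is not in the documents, so a reader cannot infer that on-treatment AML is systematically missed.
- **Tension between the two problems.** If the Follow-up Status CRF records only follow-up events, a scheduled central sample after its AML date is not expected, and late dating largely disappears. If it also accepts on-treatment AML, fewer cases are SAE-only. Late dating is the weaker part.
- **Two AML totals.** A reader might take the efficacy and safety counts as contradictory. One covers the ITT population throughout follow-up. The other is a treatment-emergent summary limited to 28 days after the last dose. They would differ even with perfect data.

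These points limit how often the problem arises. None of them brings the mandatory SAE record or the protocol's blast threshold into the endpoint. Central-first dating is defensible as a principle, but the SAP does not argue for it.

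**Conclusion.** The point holds as a defect in a stated rule. Applied as written, SAP 10.2.8 and 10.2.9 censor SAE-only and blast-only cases as AML-free and set aside an earlier CRF date when a later central diagnosis exists.

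Its size cannot be computed. The documents give no AML rate, no concordance between sources and no completion rules for the Follow-up Status CRF; the number of affected cases may be small. A reader might infer a particular loss of events, a wider interval for the hazard ratio, or a bias between arms. The documents support none of these: any loss fraction would be an assumption, and the same rule applies to both arms.

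The AML endpoints are secondary and outside the alpha-controlled sequence (SAP Section 10), so the tests of transfusion independence and OS are unaffected. The change is worth making because the data are largely in hand and AML is one of the protocol's stated reasons for the placebo arm.

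**What to change.** For the AML analysis, revise SAP 10.2.8 and 10.2.9 as follows.

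1. Define the event as the first of: central s-AML diagnosis; central marrow blasts of at least 20%; AML reported as an SAE after randomization; AML on the Follow-up Status CRF. Date it at the earliest of these.
2. List every subject whose sources disagree on occurrence or date.
3. Report the current SAP rule as a sensitivity analysis, and give the reason for the choice of sources in Section 16.
4. Leave the treatment-emergent table in 11.1.2.2 as it is, and cross-check its cases against the efficacy event list.

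The discordance listing should not be described as a blinded review. Protocol Amendment 6.0 records that the sponsor has unblinded the study and finalized the primary report. SAP Section 2 places the final AML analysis later, so the revised rule can be written for that analysis and also applied to the AML results already reported.

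The cost is SAP text and a merge of data already collected. The downside is that some locally reported cases will lack central confirmation; the discordance listing and the sensitivity analysis make their influence visible.
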